12.1 Adverse Event Definition

12.1.1 Collection of Safety Information

CTCAE term (AE description) and grade: The descriptions and grading scales found in the revised NCI Common Terminology Criteria for Adverse Events (CTCAE) version 4.0 will be utilized for AE reporting. A copy of the CTCAE version 4.0 can be downloaded from the CTEP web site (<http://ctep.cancer.gov>).

12.1.2 Attribution of the AE:

Definite – The AE *is clearly related* to the study treatment.

Probable – The AE *is likely related* to the study treatment.

Possible – The AE *may be related* to the study treatment.

Unlikely – The AE *is doubtfully related* to the study treatment.

Unrelated – The AE *is clearly NOT related* to the study treatment.

12.1.3 Recording of adverse events

At every clinical visit, the patients will be assessed for adverse events. Adverse events will be documented in patient's charts (EPIC). All adverse events will be recorded on a patient specific AE log. The AE log will be maintained by the research staff and kept in the patient's research chart. AEs will also be updated in REDCAP.

A **serious AE or reaction** is any untoward medical occurrence that at any dose:

- results in death,
- is life-threatening (defined as an event in which the patient or subject was at risk of death at the time of the event; it does not refer to an event which hypothetically

might have caused death if it were more severe),

- requires inpatient hospitalization or prolongation of existing hospitalization, (refer to note for exceptions),
- results in persistent or significant disability/incapacity,
- is a congenital anomaly/birth defect,
- is an important medical event (defined as a medical event(s) that may not be immediately life-threatening or result in death or hospitalization but, based upon appropriate medical and scientific judgment, may jeopardize the patient/subject or may require intervention (e.g., medical, surgical) to prevent one of the other serious outcomes listed in the definition above). Potential drug induced liver injury (DILI) is also considered an important medical event.

NOTE:

Pregnancy: Incidence of pregnancy is not considered a SAE; pregnancy must, however, be reported immediately to investigator. Cancer/Overdose: An overdose is defined as the accidental or intentional ingestion of any dose of a product that is considered both excessive and medically important, and must be immediately reported.

Hospitalizations (exceptions):

Criteria for hospitalizations not reported as SAEs include admissions for:

Planned as per protocol medical/surgical procedure

Routine health assessment requiring admission for baseline/trending of health status documentation (e.g., routine colonoscopy)

Medical/surgical admission for purpose other than remedying ill health state (planned prior to entry into study trial; appropriate documentation required)

Admission encountered for other life circumstance that carries no bearing on health status and requires no medical/surgical intervention (e.g., lack of housing, economic inadequacy, care-giver respite, family circumstances, administrative)

An SAE report should be completed for any event where doubt exists regarding its status of seriousness.

12.2 Reporting of Serious Adverse Events (SAEs)

Following the subject's written consent to participate in the study, all SAEs should be collected and reported, including those thought to be associated with clinical trial procedures. SAE terminology and severity grading will be based on CTCAEv4.

This is a Weill Cornell Medicine investigator-sponsored study in which the study drug will be provided by BMS. The principal investigators are responsible for reporting SAEs to the IRB, Data Safety Monitoring Board (DSMB) and the FDA or other applicable regulatory authority. The principal investigator is responsible for submitting follow-up reports for all SAEs regarding the patient's subsequent course until the SAE has resolved or until the patient's condition stabilizes (in the case of persistent impairment), or the patient dies. Reports of SAEs will be submitted to the WCM IRB and to DSMB.

The causal relationship to study drug is determined by a physician and should be used to assess all AEs. The causal relationship can be one of the following:

Related: There is a reasonable causal relationship between the study drug and the AE. The event responds to withdrawal of study drug (dechallenge), and recurs with rechallenge when clinically feasible.

Not related: There is not a reasonable causal relationship between study drug administration and the AE.

- Adverse events classified as "serious" require expeditious handling and reporting to WCM to comply with regulatory requirements.
- All SAEs whether related or unrelated to nivolumab, must be immediately reported to WCM and BMS (by the investigator or designee) within 24 hours of becoming aware of the event. If only limited information is initially available, follow-up reports are required. The original SAE form must be kept on file at the study site. All SAEs should be reported to WCM and BMS via confirmed facsimile (fax) transmission, or scanned and reported via electronic mail to:

SAE Email Address: [contact]

SAE [contact]

- Collection of complete information concerning SAEs is extremely important. Full descriptions of each event will be followed by WCM. Thus, follow-up information which becomes available as the SAE evolves, as well as supporting documentation (e.g., hospital discharge summaries and autopsy reports), should be collected subsequently, if not available at the time of the initial report, and immediately sent using the same procedure as the initial SAE report.
- An overdose is defined as the accidental or intentional ingestion of any dose of a product that is considered both excessive and medically important. For reporting purposes, WCM considers an overdose, regardless of adverse outcome, as an important medical event.
- AEs should be followed to resolution or stabilization, and reported as SAEs if they become serious. This also applies to subjects experiencing AEs that cause interruption or discontinuation of nivolumab, or those experiencing AEs that are present at the end of their participation in the study; such subjects should receive post-treatment follow-up as appropriate.
- All SAEs must be collected which occur within 100 days of discontinuation of dosing or completion of the patient's participation in the study if the last scheduled visit occurs at a later time. In addition, the Investigator should notify WCM of any SAE that may occur after this time period which they believe to be certainly, probably, or possibly related to nivolumab.

Pregnancy

Sexually active women of childbearing potential must use an effective method of birth control during the course of the study, in a manner such that risk of failure is minimized.

Before enrolling women of childbearing potential in this clinical trial, Investigators must review the guideline about study participation for WOCBP which can be found in the GCP Manual for Investigators. The topics include the following:

- General Information

- Informed Consent Form
- Pregnancy Prevention Information Sheet
- Drug Interactions with Hormonal Contraceptives
- Contraceptives in Current Use
- Guidelines for the Follow-up of a Reported Pregnancy

Prior to study enrollment, WOCBP must be advised of the importance of avoiding pregnancy during trial participation and the potential risk factors for an unintentional pregnancy. The subject must sign an informed consent form documenting this discussion.

All WOCBP MUST have a **negative** pregnancy test within 72 hours **prior** to receiving nivolumab. The minimum sensitivity of the pregnancy test must be 25 IU/L or equivalent units of hCG. If the pregnancy test is positive, the subject must not receive nivolumab and must not be enrolled in the study.

In addition, all WOCBP should be instructed to contact the Investigator immediately if they suspect they might be pregnant (e.g., missed or late menstrual period) at any time during study participation. Additionally, all pregnancies must be reported to BMS via confirmed facsimile (fax) transmission, or scanned and reported via electronic mail to:

SAE Email Address: [contact]

SAE [contact]

If following initiation of study treatment, it is subsequently discovered that a trial subject is pregnant or may have been pregnant at the time of nivolumab exposure, including during at least 6 half-lives after product administration, nivolumab will be permanently discontinued in an appropriate manner (e.g., dose tapering if necessary for subject safety). Exceptions to nivolumab discontinuation may be considered for life-threatening conditions only after consultation with the Principal Investigator or as otherwise specified in this protocol. Protocol-required procedures for study discontinuation and follow-up must be performed on the subject unless contraindicated by pregnancy (e.g., x-ray studies). Other appropriate pregnancy follow-up procedures should be considered if indicated. In addition, the course of the pregnancy, including perinatal and neonatal outcome. Infants should be followed for a minimum of eight weeks.

Follow-up information regarding the course of the pregnancy, including perinatal and neonatal outcome and, where applicable, offspring information can be reported on a Pregnancy Surveillance Form provided by BMS. Any pregnancy that occurs in a female partner of a male study participant should be reported to BMS.

Adverse events that are considered non-serious events, including lab abnormalities will be documented in REDCap database and will be reported to BMS on a regular basis. In addition to that, WCMC Datasafety monitoring committee will be reviewing the study on an annual basis and will review the adverse events collected on the study.

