1.2 Secondary Objectives

The secondary objectives of the study are: 1) to estimate the median progression free survival and the median overall survival for patients treated with immunotherapy and radiotherapy, and 2) to assess the toxicity (per CTCAE version 4.0) of patients treated with immunotherapy and radiotherapy.

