5.4 Duration of Follow Up

Patients will be followed for 3 years after removal from study or until death, whichever occurs first. Patients removed from treatment for unacceptable adverse events will be followed until resolution or stabilization of the adverse event

6 Radiation Therapy Guidelines

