6.2 Treatment

Radiotherapy is delivered by external beam using linear accelerators capable of delivering ≥ 4 megavoltage x-rays. The PTV will encompass all of the biopsied plasmacytoma lesion, and will be defined by the treating physician. The PTV will be treated daily, Monday-Friday. A dose of 30 Gy in 5 fractions of 6 Gy each is delivered, daily, to an isodose surface encompassing $\geq 90\%$ of the PTV.

Radiation Dose specification: The planning target volume receives a minimum of 90% of the prescription dose.

Treatment Machine: A linear accelerator with ≥ 4 MV x-rays is required.

Immobilization Technique: Patients will be set-up for treatment and CT scanning, and planned for treatment. The specific immobilization technique will be determined at the discretion of the treating physician.

Target Positioning Verification: Digitally acquired radiographic images will be used to verify the position of the target with respect to the treatment machine's isocenter using digitally reconstructed radiographs (DRRs) as a reference image set. Both kV and MV images may be used to verify setup.

IGRT Target Localization: In addition to the portal imaging, cone-beam CT (CBCT) images will be acquired prior to treatment for each fraction. By using IGRT to image the plasmacytoma in "real-time", the operator may automatically align the plasmacytoma with the treatment machine on each day of treatment. If shifts are made based upon the CBCT images, the portal images will be repeated.

Treatment Planning: 3D-Conformal or IMRT treatment planning is allowed. This includes "field-in-field" beams as well as the use of dynamic multi-leaf collimator (MLC) derived using inverse

planning or electronic compensator techniques. Field arrangements and technique should be chosen that satisfy the PTV dose coverage constraints and normal tissue dose constraints using Dose-Volume Histogram (DVH) analysis. By carefully selecting the gantry and table angle combinations that do not enter or exit through other organs of the body, the dose can be confined to the traditional treatment volumes.

Non-coplanar beam arrangements are encouraged, but not required.

Dose calculations with tissue inhomogeneity correction must be used.

After completion of the first course of radiotherapy + nivolumab on Day 1 (or within 24 hours of RT), the patient will start on day 15 the regimen of nivolumab 240 mg q2 weeks.

Response assessment will be performed every 2 weeks as standard of care.

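### Once the all-cause SAE window in section 12.2 closes, the late-reporting duty names nivolumab but not radiotherapy, and the plan does not say whether that window covers the 3-year follow-up

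*Combined protocol and SAP*

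**What the plan says.** Section 12.2 sets the all-cause window in one sentence with two limbs. The first is "All SAEs must be collected which occur within 100 days of discontinuation of dosing". The second is "or completion of the patient's participation in the study if the last scheduled visit occurs at a later time". The next sentence governs what follows: the investigator should notify "any SAE that may occur after this time period which they believe to be certainly, probably, or possibly related to nivolumab". Radiotherapy is not named there. The causality definition in the same section also refers to the drug alone: "Related: There is a reasonable causal relationship between the study drug and the AE". The attribution scale in section 12.1.2 is wider and refers to study treatment.

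On the regimen, section 6.2 states "A dose of 30 Gy in 5 fractions of 6 Gy each is delivered, daily", and section 5.1.2 puts this in the first week of immunotherapy. The second secondary objective in section 1.2 is "to assess the toxicity (per CTCAE version 4.0) of patients treated with immunotherapy and radiotherapy".

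On follow-up, section 5.4 states "Patients will be followed for 3 years after removal from study or until death, whichever occurs first". The calendar in section 5.1 ends with an End of Study column and has no follow-up column. No section says whether the 3-year follow-up is part of participation.

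**The concern.** The late reporting duty is limited by cause to one of the two treatments under test. Suppose a serious event first appears at the irradiated site after the all-cause window has closed, and the investigator attributes it to radiotherapy and not even possibly to nivolumab. It then falls outside both sentences of section 12.2, although the patient may still be in follow-up.

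Section 11.3.2 will report toxicity proportions with exact 95% confidence intervals, and section 11.3.5 makes patients evaluable for toxicity from first treatment without stating an end. If late radiotherapy-attributed events occur and are not reported, those proportions and the safety reports to the DSMB would leave them out, and a reader could not tell an absence of events from an absence of reporting.

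The window is also tied to when nivolumab stops, while radiotherapy is given in week 1. Patients who stop nivolumab early are therefore watched for the shortest time after the same radiotherapy.

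**Working it through.** The plan gives no figure of its own to reproduce here, so the check is a reading of the window followed by day counts.

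**Inputs.** All-cause collection after dosing stops: 100 days (12.2). Follow-up after removal: 3 years (5.4), taken as 3 × 365 = 1095 days. Radiotherapy: week 1 (5.1.2), so its start is taken as the start of nivolumab. Assumptions: 28-day cycles (the calendar doses on days 1 and 15), and removal from study on the day dosing stops.

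**Step 1: when does the window close?** The second limb of the sentence in 12.2 allows two readings.

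- *Reading A: participation ends at removal or End of Study.* Section 5.4 starts the 3 years after removal. The heading and single list of criteria in section 5.3 treat the end of therapy and removal together. Section 12.2 provides post-treatment follow-up for patients whose AEs are present when participation ends, which places that follow-up after participation. The second limb depends on a last scheduled visit, and the calendar schedules none after End of Study.
- *Reading B: participation includes the 3 years.* The Protocol Summary lists visits and follow-up together under study duration. On this reading the 100-day limit would seldom matter, because 1095 days exceeds 100.

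Reading A fits more of the text, but nothing settles the point.

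**Step 2: share of post-removal follow-up.**

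- Reading A: covered 100 / 1095 = 9.1%; not covered (1095 − 100) / 1095 = 995 / 1095 = 90.9%.
- Reading B: not covered 0%.

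**Step 3: the same window counted from radiotherapy, Reading A.** With d days on nivolumab, all-cause collection lasts d + 100 days out of d + 1095 days to the end of follow-up.

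| Time on nivolumab | d | d + 100 | d + 1095 | Covered |
|---|---|---|---|---|
| One dose | 0 | 100 | 1095 | 9.1% |
| 12 weeks | 84 | 184 | 1179 | 15.6% |
| Six 28-day cycles | 168 | 268 | 1263 | 21.2% |
| One year | 365 | 465 | 1460 | 31.8% |
| Three years | 1095 | 1195 | 2190 | 54.6% |

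The durations are scenarios only. Section 5.1.2 gives several limits on nivolumab duration that do not agree and need reconciling separately. In every row the last 995 days carry the nivolumab-only duty.

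**Step 4: which events fall in the gap?** Four kinds of event are still covered: any SAE inside the window; a late SAE thought even possibly related to nivolumab; an AE that began earlier and later becomes serious, which 12.2 follows to resolution or stabilisation and reports; and death, which enters overall survival. What remains is a new-onset, non-fatal SAE after the window, attributed to radiotherapy and not to nivolumab.

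**The case against.** The strongest reply is that other provisions already cover these events. Section 12.2 opens by saying that "all SAEs should be collected and reported, including those thought to be associated with clinical trial procedures", with no end date in that sentence, and it requires 24-hour reporting of SAEs whether or not they are related to nivolumab. Section 10.1 has REDCap capturing toxicity and adverse event data for all enrolled patients. Section 12.1.3 assesses AEs at every clinical visit. The section 11.3.2 table covers CTCAE toxicities in general, not only notified SAEs. None of these is limited to nivolumab.

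Part of this stands. These provisions rule out two inferences that a reader might draw: that the trial will collect no late radiation harm at all, and that the toxicity proportions are therefore known to be too low. Early injuries that worsen, deaths, and events recorded at a visit can all still be captured. But the general statements do not close the gap. Section 12.2 goes on to set a specific window and a specific duty after it, and that duty would be redundant if all SAEs remained reportable indefinitely. Assessment at visits does not help in a period with no scheduled visits.

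A second reply is that 100 days is not a fixed cut-off, because the same sentence extends to completion of participation. That is correct. A reader who treats 100 days as unconditional goes beyond the text, and this is why the uncovered share must be given as about 91% or 0%.

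A third reply is that radiotherapy toxicity is not an objective in its own right. That is also correct: section 1.2 concerns patients given the combination, and the documents state no late-effects objective. The gap still matters, because radiotherapy is part of that combination.

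**Conclusion.** The point holds in a limited form. Once the all-cause window closes, the only stated duty is for nivolumab-related SAEs, so the rule leaves out radiotherapy. On the more natural reading, new-onset, non-fatal late SAEs attributed to radiotherapy alone have no clear reporting duty for up to about 91% of the 3-year follow-up. If follow-up counts as participation, the figure is 0%. The 91% assumes removal on the day dosing stops. Counted from radiotherapy, all-cause collection lasts about 100 days after one dose, 268 days after six cycles and 465 days after one year of nivolumab.

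All treated patients, up to 30, come under the rule. How many events it would miss cannot be stated, because the documents give no late radiation event rate. Any understatement in section 11.3.2 or in DSMB reports is therefore conditional on such events occurring. The change is worth making because the omission is plain, the ambiguity is wide and the remedy is small.

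**What to change.** 1. In the late-SAE sentence of section 12.2, after the reference to nivolumab, add the words *or to protocol radiotherapy*. Leave the rest unchanged. The nivolumab duty has no end date now, and the edit should not limit it to 3 years.
2. Reconcile sections 5.4 and 12.2 by stating whether the 3-year follow-up counts as participation, and therefore when all-cause SAE collection ends.
3. In section 11.3.2, list late treatment-related SAEs separately from those inside the all-cause window, so that the toxicity proportions keep a clear time frame.

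The cost is a few lines of text, a few more late reports, and possibly a higher reported toxicity rate. The follow-up period and the reporting route already exist. One limit remains: with no follow-up visits in the calendar, the wording creates a duty to report but not systematic detection, so capture will depend on the investigator becoming aware of the event.

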12.3 Off Study Criteria

1. Intercurrent illness that prevents further administration of treatment,
2. Unacceptable toxicity (defined in Section 15),

3. Patient decides to withdraw from the study, or
4. General or specific changes in the patient's condition render the patient unacceptable for further treatment in the judgment of the investigator.
5. Authorized Physicians must notify the data manager and Principle Investigator when a patient is taken off study.

13 PROHIBITED AND RESTRICTED THERAPIES DURING THE STUDY

13.1 Prohibited Therapies

Patients in this study may not use vaccines for the treatment of cancer for up to one month before the first dose of nivolumab. Concomitant systemic or local anti-cancer medications or treatments are prohibited while receiving study treatments.

- Patients may not use any of the following therapies during the study:
- Any non-study anti-cancer agent (investigational or non-investigational);
- Any other investigational agents;
- Any other CTLA-4 or anti PD-1 or PD-L1 inhibitors or agonists;
- Immunosuppressive agents;
- Chronic systemic corticosteroids.

13.2 Data and Safety Monitoring Plan (DSMP)

Study monitoring

There will be monthly reports generated for study accrual, observed AEs, and data timeliness. The study team will review these reports. In addition, the study will undergo periodic review by the Weill Cornell data safety and monitoring board (DSMB).

DSMB Safety Review

The protocol will be reviewed by the Data Safety Monitoring Board (DSMB) on a semi-annual basis. Safety reports will be submitted to the DSMB every six months.

ADMINISTRATIVE SECTION

Compliance with the Protocol and Protocol Revisions

The study will be conducted as described in the final approved protocol. Documentation of approval signed by the chairperson or designee of the IRB(s) will be sent to the WCM protocol manager.

All revisions (protocol amendments, administrative letters, and changes to the informed consent) will be submitted to the WCM protocol manager. The Investigator will not implement any deviation or change to the protocol without prior review and documented approval/favorable opinion from the IRB of an Amendment, except where necessary to eliminate an immediate hazard(s) to study

patients.

